## **1.8 Efficacy evaluation**

### **1.8.1 Variables**

The primary objective of the study is to assess long-term safety and tolerability of secukinumab in subjects with moderate to severe chronic plaque-type psoriasis who completed treatment in the core studies CAIN457A2304 and CAIN457A2307.

The analysis of the secondary efficacy variables will be based on the FAS.

The main secondary efficacy analysis is maintenance of response. Maintenance of response is defined as follows:

- for subjects in the fixed interval regimens, maintenance of response is defined as PASI 75 response at Weeks 104 and 156
- for subjects in the start of relapse regimens maintenance of response is defined as

- PASI 75 response at Weeks 92 and 144 for subjects who do not require active treatment at Week 92 or 144 and
- PASI 75 response at Weeks 104 and 156 for subjects who do require active treatment at Week 92 or 144.

In order to identify whether active treatment was applied at Weeks 92 and 144 the following will be utilized:

- Visit windows as in Table 1-8 (as for efficacy with date of randomization as day 1) will be applied to dosing date.
- The analysis visit Weeks 92 and 144 will be identified for dosing. The PASI assessment for the corresponding CRF visit will be selected.
- If no dosing for analysis visit Weeks 92 and 144 is identified, it is concluded that no active treatment was given. Therefore, the PASI 75 response status of the analysis visit Weeks 92 and 144 will be considered.
- For subjects with assigned dosing records at Weeks 92 and 144 but for which no corresponding PASI assessment can be assigned, non-responder imputation will be performed

Apply visit windowing to the dosing dates then find the weeks 92 and 144 dosing date. With this dosing date search for the corresponding PASI data with the same date. If there was no AIN dosing at these weeks 92 and 144 then it shall be assumed that the PASI response at Weeks 92 and 144 will be taken for the maintenance of response parameter.

[Table 1-10](#) lists the variables for the final analysis.

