For subjects willing to self-inject, the first use at enrollment visit (Week 52) will take place under guidance and the supervision of one site staff member. At the enrollment visit (Week 52) the site staff will walk subjects through the “Instructions For Use” on how to self-inject via PFS. At the following visits, subjects will receive the PFS and instructions at the study site to follow on their own.

NOTE: The needle cover of the syringe contains dry rubber (latex), which should not be handled by persons sensitive to this substance.

During the treatment period from Week 52 until Week 256, subjects will receive a maximum of 104 study treatment injections (2 injections of secukinumab 150 mg PFS and/or placebo PFS at each visit). The actual number of study treatment injections will depend on the treatment assigned. All subjects will receive 52 study treatment injections between Week 52 and Week 152 (2 injections of secukinumab 150 mg PFS and/or placebo PFS at each visit); between Week 156 and 256 subjects could receive as many as 52 study treatment injections (2 injections of secukinumab 150 mg PFS every four weeks) or as few as 0 study treatment injections (SoR treated subjects who do not meet start of relapse criteria at any point).

At study visits when pre-dose blood samples have to be drawn ([Table 6-1](#)), the study treatment will be injected to the subject only after the blood samples have been taken.

At each visit, all study assessments, including the completion of Patient Reported Outcomes (PROs), should be completed prior to the self injection of study treatment.

After Week 256, no further study treatment will be administered during the treatment period. In addition, no study treatment is administered during the follow-up period and follow-up 2 period.

The subject should be instructed to contact the investigator if he/she is unable for any reason to attend a study visit as scheduled.

All dates, times of injections, mode of injection (self or by study site staff) during the study must be recorded on the Dosage Administration Record eCRF. Immediately before dispensing the package for injection, investigator staff will detach the outer part of the label from the packaging and affix it to the source document (Drug Label Form) for that subject's unique subject number.

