5.5.12 Early study termination

The study can be terminated at any time for any reason by Novartis. Should this be necessary, the patient should be seen as soon as possible and properly managed for a prematurely withdrawn patient. The investigator may be informed of additional procedures to be followed in order to ensure that adequate consideration is given to the protection of the patient's interests. The investigator will be responsible for informing IRBs and/or ECs of the early termination of the trial.

6 Visit schedule and assessments

[Table 6-1](#) Assessment Schedule lists all of the assessments and indicates with an "x" when the visits are performed.

Subjects should be seen for all visits on the designated day within the allowed “visit window” specified below or as close to it as possible.

During the treatment period, subjects may be seen at an unscheduled visit, e.g. if they experience deterioration of psoriasis, or AEs that in the opinion of the investigator need intervention or repeated laboratory testing. During these unscheduled visits, study treatment will NOT be administered. A visit window of “±5” will be allowed for Week 52 to Week 260 during the treatment period during the follow-up period or as close to it as possible.

Subjects who discontinue study treatment will continue to be followed for safety assessments. They are not considered withdrawn from the study.

Subjects who discontinue study treatment before completing the study, and those who prematurely withdraw from the study for any reason should be scheduled for a study visit 4 weeks after their last study treatment administration, at which time all the assessments listed for EOT (Week 260) will be performed (see [Section 5.5.10](#)). Subjects will return to the study site for further assessments as indicated under the follow-up visits (Weeks 264 and 268) (see [Section 3.1](#)).

Only subjects who prematurely discontinued study treatment should enter follow-up 2 period after completion of follow-up visits (Weeks 264 and 268). Follow-up 2 period includes telephone calls every 3 months until 4 years from the time subjects have been enrolled into CAIN457A2304E1 as well as potential unplanned assessments e.g physical examinations, vital signs and laboratory assessments during this time.

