³ To be done for female subjects of childbearing potential for whom local urine pregnancy test at end of maintenance period (Week 52) of core study is positive. The study drug treatment should not be given until the results confirm that subject is not pregnant.

⁴ If there is a positive urine pregnancy test, study treatment must be withheld and a serum pregnancy test must be done at the same visit.

⁵ Samples will be shipped by the sites and stored by the central laboratory. Samples will be shipped to reference laboratories for analysis. Each PK and IG sample is to be collected pre-dose for visits from Week 52 to Week 256.

⁶ An unscheduled IG and or PK sample is collected only to replace an IG or PK sample not taken at a regular scheduled visit. (If an IG sample is taken, a PK sample must accompany the IG sample.)

⁷ Unscheduled rebound assessment only to be done for an unscheduled visit that occurs during the treatment free follow-up period following a study drug discontinuation.

⁸ During this extension study, the HAQ-DI is completed only by subjects from core study CAIN457A2304 who have a history of psoriatic arthritis at the core baseline visit.

⁹ IGA eCRF only needs to be completed at visits when IGA is required

¹⁰ In subjects treated per SoR regimen, investigational treatment should only be dispensed and administered to patients meeting protocol-defined SoR treatment criteria

¹¹ During follow-up 2 period unscheduled visits may include unplanned assessments like physical examinations, vital signs and laboratory assessments if investigator considers this necessary.

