6.4 Efficacy

All efficacy assessments should be performed prior to administration of study treatment.

It is important to **perform the IGA before the PASI**, as the knowledge of PASI scoring can potentially influence how the evaluator scores the IGA. Therefore, the following order should be applied when performing the efficacy assessments during study visits:

- Investigator's Global Assessment (IGA mod 2011; scale from 0 – 4)
- Psoriasis Area and Severity Index (PASI; score from 0 – 72)
- Rebound assessment

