- **Start of relapse:** loss of $\geq 20\%$ of the maximum PASI gain in CAIN457A2304 or CAIN457A2304E1 (compared to baseline of the core study) achieved at any time before the visit at which the assessment is made and loss of PASI 75 response
- **PASI Partial response:** Subjects achieving at least 50%, but less than 75% reduction of PASI compared to baseline (i.e PASI 50 but not a PASI 75 response)
- **PASI Non response:** Subjects achieving less than 50% reduction of PASI compared to baseline

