9.5 Analysis of secondary variables

9.5.1 Efficacy variables

Maintenance of response

Maintenance of response will be defined analogously as in the primary endpoint in CAIN457A2304, but for week 104 and 156, i.e. PASI 75 response

- at Weeks 104 and 156, for subjects in the fixed interval regimens, or
- at Weeks 92 and 144, for subjects in the retreatment at start of relapse regimen who do not require active treatment at Week 92 or 144, respectively, or
- at Weeks 104 and 156, for subjects in the retreatment at start of relapse regimen who do require active treatment at Week 92 or 144, respectively.

Summary statistics for maintenance of response at Week 104 and 156 will be presented in contingency tables and will include absolute and relative frequencies. Confidence intervals for response rates will be derived as well based on the score method including continuity correction ([Newcombe 1998](#)).

PASI 50, PASI 75, PASI 90, PASI 100 and IGA 0 or 1 response over time

Summary statistics for PASI 50, PASI 75, PASI 90, PASI 100 and IGA 0 or 1 response by visit will be presented in contingency tables and will include absolute and relative frequencies. Confidence intervals for response rates will be derived as well based on the score method including continuity correction ([Newcombe, 1998](#)).

PASI score over time

Summary statistics will be provided for absolute PASI scores as well as for percent change from baseline by visit and treatment group. Figures will also be provided.

IGA mod 2011 score over time

Summary statistics for the IGA mod 2011 score over time will be presented by visit and treatment group in contingency tables.

Relapse

The number and percentage of subjects experiencing relapse will be presented by visit and treatment group.

Rebound

Rebound is defined as a worsening of PASI of > 125% of the value at baseline (core study), or new pustular, erythrodermic or more inflammatory psoriasis occurring within 8 weeks of stopping therapy (i.e., if this definition is fulfilled at more than 8 weeks after last study treatment administration, this is not defined as rebound). The number and percentage of subjects experiencing rebound will be presented by visit and treatment group.

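### SAP 1.8.1 scores a start-of-relapse subject who needed active drug at Week 92 or 144, was assessed but not dosed, and stayed on treatment at the wrong visit, almost always as a non-responder

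*SAP*

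**What the plan says.** Protocol 2.2 and 9.5.1 score FI subjects on PASI 75 at Weeks 104 and 156. A SoR subject who needs no active drug at Week 92 (or 144) is scored at that visit. Scoring moves to Week 104 (or 156) "for subjects in the retreatment at start of relapse regimen who do require active treatment at Week 92 or 144, respectively". SAP 1.8.1 and 1.8.7 repeat this criterion of need.

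SAP 1.8.1 then gives an algorithm whose stated aim is to find out whether active drug was *applied*. Dosing dates are placed in the Table 1-8 windows, and "If no dosing for analysis visit Weeks 92 and 144 is identified, it is concluded that no active treatment was given". The section's closing paragraph makes clear that active drug is meant: "If there was no AIN dosing at these weeks 92 and 144 then it shall be assumed that the PASI response" at those weeks supplies the endpoint. The only fallback covers the reverse case, a dosing record with no matching PASI, which is imputed as non-response.

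Four other provisions bear on the point:

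- **Placebo:** SoR subjects not in relapse receive placebo injections (Protocol 5.2), and "All subjects will receive 52 study treatment injections between Week 52 and Week 152" (Protocol 5.5.4).
- **Order of procedures:** "All efficacy assessments should be performed prior to administration of study treatment" (Protocol 6.4).
- **Relapse and retreatment:** start of relapse is a loss of at least 20% of the maximum PASI gain "achieved at any time before the visit at which the assessment is made and loss of PASI 75 response" (Protocol 6.4.2). Retreatment stops once PASI 75 is regained (Protocol 5.2).
- **Available data:** the PASI eCRF calculates start-of-relapse status at each visit, and IRT assigns medication from it (Protocol 6.4.2).

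SAP 1.1.1 lists other changes to the maintenance analysis but not this one.

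**The concern.** *Required* and *applied* come apart whenever a needed dose is not given. Because non-relapsing SoR subjects get placebo, a subject who needs no drug at Week 92 should still have an injection record, so a missing record is not evidence that drug was not needed. Yet the algorithm treats it as such and fixes the endpoint at the visit where the subject is in relapse.

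The SAP calls maintenance of response its main secondary efficacy analysis, and it serves the objective of comparing SoR with FI. An FI subject who misses the Week 92 dose is still scored at Week 104. A SoR subject in relapse who misses the same dose loses the chance to be scored there.

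**Working it through.** **1. Is an injection due at every visit?** Visits from Week 52 to Week 152 every four weeks: (152 − 52)/4 + 1 = 26. At two injections each, 26 × 2 = 52, which reproduces the figure in Protocol 5.5.4.

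**2. When is a dose not found?** The SAP Table 1-8 windows are Day 632–659 (659 − 632 + 1 = 28 days) and Day 996–1023 (1023 − 996 + 1 = 28 days). A late dose still inside the window is found. The problem needs a PASI in the window and no active dose there. This can happen because PASI precedes dosing, and because PASI may also be taken at an unscheduled visit, where no drug is given: "During these unscheduled visits, study treatment will NOT be administered" (Protocol 6).

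**3. Is PASI 75 absent at that visit?** A SoR subject requires active drug in one of two situations:

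- the start-of-relapse criteria are met at the visit, which includes loss of PASI 75;
- they were met earlier and PASI 75 has not been regained, so it is still absent.

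Either way the subject is a non-responder on the PASI that sets the status. The one gap is that the analysed PASI is the one closest to the target day (SAP 1.4.5 and Table 1-9), which need not be the one that triggered retreatment. Hence *almost always*.

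**4. Where should the subject be scored?** Week 92 is Day 92 × 7 + 1 = 645 and Week 104 is Day 104 × 7 + 1 = 729, which is 84 days or 12 weeks later. The same gap separates Day 1009 from Day 1093. Three doses fall before the pre-dose Week 104 PASI (Weeks 92, 96, 100). Without the first, at most two are given, so later response may be less frequent than after full retreatment.

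**5. Weight of one subject.** Protocol 9.7: 918 × 0.95 × 0.85 = 741 eligible, and 741 × 0.80/4 = 148 per arm, as stated. Scaled to actual enrolment: 148 × 675/740 = 135, assuming the shortfall was even across groups.

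- 100/148 = 0.68 points
- 100/135 = 0.74 points
- As-observed denominators are smaller. About 108 of 675 had discontinued by Amendment 1. If spread evenly, 135 × (675 − 108)/675 = 113, and 100/113 = 0.88 points.

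**6. Illustrative size.** Understatement = 100 × k × r / n, where k is the number of continuing SoR subjects per arm in relapse with a PASI and no dose, and r is the share with PASI 75 at Week 104 or 156. The documents give neither. Assume k = 1 to 4 and r = 0.30 to 0.70.

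- Low: 100 × 1 × 0.30/148 = 0.20 points
- High: 100 × 4 × 0.70/135 = 2.07 points

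A looser set of assumptions gives 100 × 0.3 × 0.01 × 0.5 = 0.15 to 100 × 0.7 × 0.10 × 0.9 = 6.3 points. It takes 30–70% requiring drug, 1–10% of those assessed but undosed, and 50–90% responding later. Its upper end implies 0.7 × 0.10 × 148 = 10 undosed subjects per arm at a single visit, which is hard to reconcile with a protocol that allows almost no interruptions.

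**The case against.** **Dosing is a close proxy by design.** PASI is entered before IRT is called, status is calculated from it, and medication follows status. Protocol 5.5.5 permits no interruptions apart from the pregnancy rule. This stands, and it is why the number affected should be very small.

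**Pregnancy is a weak example.** "If there is a positive urine pregnancy test, study treatment must be withheld" (Protocol Table 6-1, note 4) does produce an assessed but undosed visit. But a positive serum test leads to discontinuation, so only a urine result not confirmed by serum fits. This also stands.

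**Discontinuation is another cause.** A reader might infer that every missing record is a missed or withheld dose, and that each affected subject would otherwise have taken a Week 104 or 156 result. The documents do not support that. Early discontinuers have end-of-treatment assessments about four weeks after the last dose (Protocol 3.1 and 5.5.9). A last dose at Week 88 puts that PASI at Week 92 with no dose. Follow-up visits come 4 and 8 weeks later, at Weeks 96 and 100, before Week 104, and follow-up assessments are excluded anyway (SAP 1.1.1 and 1.8.4). These subjects normally have no eligible Week 104 PASI. Moving them there would remove observed failures from the as-observed analysis and raise the SoR rate artificially.

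**Little depends on it, and it is late.** The primary objective is safety, there is no formal testing (SAP 1.8.3), and four interim analyses are done (SAP 1.12). A 95% interval for one arm has a half-width of about 1.96 × √(0.25/148) = 8.1 to 1.96 × √(0.25/135) = 8.4 points at a 50% rate. This limits the importance and calls for open disclosure. It does not make the rule agree with the definition.

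**Without the dose, Week 104 does not measure retreatment.** This does not hold. FI subjects who miss a dose are still scored at Week 104, and the criterion as written is need, not receipt.

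**Conclusion.** The point holds for continuing subjects only. The SAP 1.8.1 algorithm departs from the criterion stated in Protocol 9.5.1 and in the SAP itself. A SoR subject in relapse who has a PASI in the Week 92 or 144 window, is not dosed there and stays on study treatment is scored 12 weeks early, almost always as a non-responder. For this group the error runs one way, against SoR.

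The size is about 0.7 points per misclassified later responder, somewhat more on an as-observed denominator, and 0.2 to 2.1 points under the assumed 1 to 4 subjects and 30–70% later response. If PASI is also missing at the visit, the subject is missing or multiply imputed and the problem does not arise. The documents do not support reading this as a material distortion of the SoR versus FI comparison. It is a minor but plain mismatch in a descriptive endpoint, worth correcting because the correction is cheap.

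**What to change.** In SAP 1.8.1, for Week 92 and Week 144 separately:

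- **SoR subjects still on study treatment:** classify as requiring active treatment if the start-of-relapse criteria are met at that visit, or were met earlier and PASI 75 has not been regained. Take this from the eCRF start-of-relapse status and PASI history, not from the dosing record. Score these subjects at Week 104 (or 156) whether or not the dose was given, and the rest at Week 92 (or 144). A missing Week 104 or 156 PASI follows the SAP's existing as-observed and multiple imputation rules, as in the FI arms.
- **SoR subjects who had discontinued by Week 92 (or 144):** keep scoring on the observed Week 92 (or 144) PASI as now, so that observed failures stay in.

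List the change in SAP 1.1.1. Report per arm how many subjects change category, with continuers and discontinuers shown separately, and note any difference from the interim outputs.

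The cost is one rule, one line in SAP 1.1.1 and minor reprogramming. No new data are needed. Because the change comes after unblinding at Week 156 and after the interims, the report should show the counts openly.

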### **1.1.1 Changes to statistical methods planned in the protocol**

Table 1-11 is a modified version of table 6-3 of the protocol to clearly indicate that the area score is derived from area% without rounding.

For the maintenance of response analysis, the non-responder imputation method defined in the protocol will be dropped. The as observed result for PASI and IGA responses will be primarily looked into; the multiple imputation method will be provided as well. Assessment during follow-up period excluded.

In addition to the planned analysis on adverse events, by 1-year interval analysis on the adverse events will be provided in order to assess the occurrence of adverse events over time.

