### **1.8.4 Handling of missing values/censoring/discontinuations**

As observed value (Follow-up assessment excluded) will be reported primarily for both efficacy and PROs.

Response variables based on PASI score and IGA mod 2011 categories will be imputed with multiple imputation (MI) (Follow-up assessment excluded) as secondary analysis method. Summary tables for PASI scores and IGA mod 2011 categories will also be imputed using MI. Other response variables (e.g. DLQI 0 or 1 achievement) will be imputed with LOCF (Follow-up assessment excluded).

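### SAP 1.8.1 still orders non-responder imputation in one step of the maintenance-of-response derivation, although SAP 1.1.1 drops that method and SAP 1.8.4 does not list it

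*SAP*

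**What the plan says.** Protocol 9.4.3 scores every missing PASI-based response for maintenance of response as non-response, whatever the reason for the gap.

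SAP 1.1.1 changes this. For the maintenance analysis, "the non-responder imputation method defined in the protocol will be dropped"; as-observed results come first, multiple imputation (MI) is also provided, and follow-up assessments are excluded.

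SAP 1.8.4 sets the general rule: "As observed value (Follow-up assessment excluded) will be reported primarily for both efficacy and PROs". MI is the secondary method for responses based on PASI and IGA, and last observation carried forward is kept for other response variables. Non-responder imputation does not appear. SAP 1.8.7 repeats the endpoint definition and adds no missing-data rule.

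SAP 1.8.1 calls maintenance of response the main secondary efficacy analysis. FI subjects are judged at Weeks 104 and 156. SoR subjects are judged at Weeks 92 and 144 if they did not need active treatment then, and at Weeks 104 and 156 if they did. The section then lists steps for finding out whether active treatment was given at Weeks 92 and 144:

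- Dosing dates are mapped to visit windows and the Week 92 and 144 doses identified. "The PASI assessment for the corresponding CRF visit will be selected".
- If no dosing is found, "it is concluded that no active treatment was given", and the Week 92 or 144 PASI 75 status is used.
- For subjects with dosing records at those weeks "but for which no corresponding PASI assessment can be assigned, non-responder imputation will be performed".

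**The concern.** The last of these steps applies, to the same endpoint, the method that SAP 1.1.1 says is gone. Protocol 9.4.3 already covered every missing PASI response for maintenance of response. So wherever the endpoint PASI is missing, the bullet is a piece of what was dropped, and it is not declared as an exception.

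The secondary objective sets SoR against FI on this endpoint. A failure rule that works through a step needed only for SoR would treat missing data differently in the two regimens without a stated reason, and always to the disadvantage of SoR. Two programmers could also report different SoR rates from the same data, depending on which section they followed.

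**Working it through.** **What the bullet leaves open.** Three things are not stated.

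1. *Which doses.* The neighbouring steps equate no dosing with no active treatment, and the closing paragraph begins: "If there was no AIN dosing at these weeks 92 and 144 then it shall be assumed". Under the blind (Protocol 5.2), SoR subjects not in relapse receive placebo injections every four weeks, so a subject attending as planned always has some injection recorded. The natural reading is that dosing records means active doses, but the text does not say so.
2. *Which visit is set to failure.* It could be the maintenance endpoint, or only the Week 92 or 144 response.
3. *Which analysis.* The bullet does not say whether it applies to as-observed, MI or both.

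**Consequences for one SoR subject** with a Week 92 dosing record and no PASI at that visit (Weeks 144 and 156 work the same way):

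| Case | Under SAP 1.1.1 and 1.8.4 | SAP 1.8.1, failure written to the endpoint | SAP 1.8.1, failure written to Week 92 only |
|---|---|---|---|
| A. Active dose; Week 104 PASI 75 response observed | Responder | Non-responder | Responder |
| B. Active dose; Week 104 PASI missing | Left out (as observed) or MI | Non-responder | Left out or MI |
| C. Placebo dose, if such doses count; Week 92 is the endpoint | Left out or MI | Non-responder | Non-responder |

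In no cell does the bullet raise the SoR rate. In some it lowers it; in others it does nothing.

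**Size.** No figure in the plan depends on this point, and the number of affected subjects, m, is not given. For scale I use the planned arm size in Protocol 9.7, which reproduces: 918 × 0.95 × 0.85 × 0.80 / 4 = 148.3, stated as about 148.

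*Cases B and C.* Let n be the arm size including the m affected subjects, and p the assumed rate among the rest. The as-observed rate is p. With the m counted as failures it is p(n − m)/n, a fall of pm/n.

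| n = 148 | p = 50% | p = 70% | p = 90% |
|---|---|---|---|
| m = 1 | 0.3 points | 0.5 | 0.6 |
| m = 5 | 1.7 | 2.4 | 3.0 |
| m = 10 | 3.4 | 4.7 | 6.1 |

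If only n = 100 contributed, m = 1 would give 0.5 to 0.9 points. A smaller denominator than planned is realistic: 675 subjects enrolled against about 740 expected.

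*Case A, failure written to the endpoint.* Each observed responder scored as a failure costs 1/148 = 0.68 points.

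*Yardstick.* At an assumed 80% with n = 148, the 95% score interval with continuity correction runs from 72.3% to 85.9% by the formula printed in SAP 2.2.1. The lower-limit formula printed in SAP 2.3.1 differs in one sign and gives 72.5%; this does not matter here. One affected subject is small beside that width.

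**The case against.** The strongest defence is that SAP 1.1.1 drops the general method defined in the protocol, while the 1.8.1 bullet is a specific derivation step for a mismatch between dosing and PASI records. A programmer could apply the specific step and use as-observed or MI everywhere else. That is workable, so it would be too strong to say that the sections cannot be executed together. It does not remove the conflict: the protocol's rule already covered any missing PASI response for this endpoint, and the SAP nowhere labels the bullet an exception.

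The defence is also right that the rule should hardly ever apply. Protocol Section 6 has PASI entered in the eCRF before IRT is contacted, and Protocol 6.4.2 has IRT assign medication from the relapse status calculated there. A properly assigned active dose presupposes the very PASI said to be missing.

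A reader might infer three stronger things that the documents do not support:

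- *That SAP 1.8.4 also drops the method.* It mentions neither non-responder imputation nor maintenance of response; it simply does not list the method. Only 1.1.1 drops it.
- *That SoR subjects with an observed Week 104 or 156 response will be overridden to failure.* This is case A under one reading. If the failure is written only to Week 92 or 144, an actively dosed subject's endpoint is untouched.
- *That the bullet is expressly confined to SoR.* It names no regimen, and FI subjects are also dosed at Weeks 92 and 144. The SoR scope is inferred from the purpose of the steps, which have no role in the FI endpoint.

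**Conclusion.** The inconsistency stands: for this endpoint SAP 1.1.1 drops non-responder imputation without exception, 1.8.4 offers only as-observed and MI, and 1.8.1 still orders non-responder imputation in one situation. Read in context, the bullet acts on SoR rates only and can lower but not raise them.

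The severity is minor. The effect is expected to be very small, though the documents do not allow a count. The per-subject figures rest on the planned arm size and assumed response rates, and the 0.68-point figure also rests on the override reading. SAP 1.8.3 plans no hypothesis test, so no type I error is at issue. The documents give no ground for saying that the comparison of SoR with FI is materially distorted.

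**What to change.** Delete the non-responder bullet in SAP 1.8.1. As-observed and MI then apply alike to both regimens, at the visit that defines each subject's endpoint in SAP 1.8.1 and 1.8.7. The cost is one bullet of SAP text, with no new data, table or analysis.

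If the sponsor intends the bullet, declare it as an exception in SAP 1.1.1 and 1.8.4. State which visit is set to failure, whether placebo doses count, and whether it applies to as-observed, MI or both. Extending it to both regimens at the endpoint visit would be more than a wording change, because it would largely restore the method that 1.1.1 dropped.
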